### 7.9.10. Patient Questionnaires

The following questionnaires will be completed by patient prior to all other assessments scheduled for the visit day at the days indicated in Table 1.

- **WOMAC® LK 3.1**
- **KOOS - Quality of Life Subscale (Q1-Q4)**
- **GPAQ**

### 7.9.11. Daily Activity

Steps per day will be captured using a measured function device. Patients will be provided with a device at the Screening visit to be worn for at least 7 days prior to Baseline/Day 1 through Week 12. The site will confirm patient compliance with wearing the device to capture steps per day data at each patient visit from Day 1 through Week 12.

### **7.9.12. Synovial Fluid Aspiration**

Synovial fluid samples for potential future biomarker evaluation will be obtained from all patients via aspiration on Baseline/Day 1 prior to study medication administration and the week at which the second dose is administered prior to study medication administration (if the patient is eligible to receive a second dose). Patients that are not eligible to receive a second dose will not have synovial fluid drawn at their final study visit. The injector/aspirator will attempt to aspirate synovial fluid from the index knee using sterile technique. The volume of the synovial fluid obtained will be recorded in the eCRF. If no synovial fluid is obtained then 0 mLs should be recorded. Procedures for sample collection, handling, storage and shipment will be described in the Study Laboratory Manual. The synovial fluid samples will be preserved for potential future analyses of biomarkers that may contribute to the pathogenesis of OA and/or be associated with responsiveness to FX006 treatment.

### **7.9.13. Treatment Administration**

At Baseline/Day 1 and the week at which the second dose is to be administered (if the patient is eligible to receive a second dose), the following will occur:

- Study medication will be prepared by the pharmacist/coordinator (Refer to the Pharmacy Binder for instructions on how to prepare FX006).
- Synovial fluid will be aspirated from the index knee just prior to administration of study medication (refer to Section [7.9.12](#) for more details of the synovial fluid aspiration).
- The injector/aspirator will perform the IA injection of the study medication (refer to Section [7.5.8](#) for instructions).

### **7.9.14. Review of Adverse Events and Concomitant Medications**

After receiving study medication, the patient will be monitored for any AEs. Review of any Concomitant Medications will also be performed and documented in source documentation. Refer to Section [8.1](#) for further information in regard to reporting of AEs. Refer to Section [7.6](#) for further information in regard to allowed and restricted concomitant medication.

## 8. CLINICAL SAFETY ASSESSMENTS

Safety evaluations will be based on the assessment of AEs occurring after the initiation of study medication on Day 1 through the last study visit. Results of clinical safety assessments are to be recorded in the patient's medical records and transcribed to the appropriate eCRF, including the AE eCRF for clinically significant findings.

### 8.1. Adverse Events

#### 8.1.1. Definitions

An AE is any untoward medical occurrence in a patient or clinical investigation patient administered a pharmaceutical product and that does not necessarily have a causal relationship with this treatment.

An AE can therefore be:

- Any unfavorable and unintended sign (including an abnormal laboratory finding), symptom, or disease temporally associated with the use of a medicinal (investigational) product, whether or not related to the medicinal (investigational) product.
- Any clinically significant abnormality found on an ECG, laboratory test or physical examination.
- Any worsening (i.e., any clinical significant adverse change in frequency and/or intensity) of a preexisting condition, which is temporally associated with the use of the medicinal (investigational) product, is also an AE.

An SAE is any untoward medical occurrence that at any dose:

- Results in death,
  - This serious criterion applies if the patient's death is a direct outcome of a reported AE.
- Is life-threatening,
  - This serious criterion refers to an event in which the patient was at substantial risk of death at the time of the event; it does not refer to an event which hypothetically might have caused death if it were more severe.
- Requires inpatient hospitalization or prolongation of existing hospitalization,
  - This serious criterion applies if the reported AE requires at least a 24-hour inpatient hospitalization or, if in the opinion of the Principal Investigator, prolongs an existing hospitalization. A hospitalization for an elective procedure or a routinely scheduled treatment is not an SAE by this criterion because a "procedure" or a "treatment" is not an untoward medical occurrence.

- Results in permanent or significant disability/incapacity, or
  - This serious criterion applies if the “disability” caused by the reported AE results in a substantial disruption of the patient’s ability to carry out normal life functions.
- Is a congenital anomaly/birth defect.
  - This serious criterion applies if a patient exposed to a medicinal (investigational) product gives birth to a child with congenital anomaly or birth defect.

Medical and scientific judgment should be exercised in deciding whether expedited reporting is appropriate in other situations, such as important medical events that may not be immediately life-threatening or result in death or hospitalization but may jeopardize the patient or may require intervention to prevent one of the other outcomes listed in the definition above. These should also usually be considered serious.

Examples of such events are intensive treatment in an emergency room or at home for allergic bronchospasm; blood dyscrasias or convulsions that do not result in hospitalization; or development of drug dependency or drug abuse.

### **8.1.2. Evaluating and Recording of Adverse Events**

At each visit all AEs that occur from the time of treatment and throughout a patient’s study participation that are observed, elicited by the site personnel, or reported by the patient, will be recorded in the source documentation and appropriate section of the AE eCRF and evaluated by an assessor.

Minimum information required for each AE includes type of event, duration (start and end dates), severity, seriousness, causality to investigational medicinal product, action taken, and outcome.

Severity of AEs will be graded by the Principal Investigator using the Common Terminology Criteria for AEs (CTCAE) version 4.0 (refer to the Study Manual or [http://ctep.cancer.gov/protocolDevelopment/electronic\\_applications/ctc.htm](http://ctep.cancer.gov/protocolDevelopment/electronic_applications/ctc.htm)).

For AEs not listed in the CTCAE, the following definitions should be used:

Grade 1	Mild Symptomatic or mild symptoms Clinical or diagnostic observations only Intervention not indicated
Grade 2	Moderate Minimal, local or noninvasive intervention indicated Limiting age-appropriate instrumental activities of daily living (ADL)*
Grade 3	Severe or medically significant but not immediately life-threatening Hospitalization or prolongation of hospitalization indicated Disabling Limiting self care ADL**
Grade 4	Life-threatening consequences Urgent intervention indicated
Grade 5	Death related to AE

\*Instrumental ADL refer to preparing meals, shopping for groceries or clothes, using the telephone, managing money, etc.

\*\*Self care ADL refer to bathing, dressing and undressing, feeding self, using the toilet, taking medications, and not bedridden.

The relationship of the AE to the investigational medicinal product should be specified by the Principal Investigator, using the following definitions:

1. Not Related: Concomitant illness, accident or event with no reasonable association with treatment.
2. Unlikely: The reaction has little or no temporal sequence from administration of the investigational medicinal product, and/or a more likely alternative etiology exists.
3. Possibly Related: The reaction follows a reasonably temporal sequence from administration of the investigational medicinal product and follows a known response pattern to the suspected drug; the reaction could have been produced by the study medication or could have been produced by the patient's clinical state or by other modes of therapy administered to the patient.
4. Probably Related: The reaction follows a reasonable temporal sequence from administration of study medication; is confirmed by discontinuation of the study medication or by rechallenge; and cannot be reasonably explained by the known characteristics of the patient's clinical state.
5. Definitely Related: The reaction follows a reasonable temporal sequence from administration of study medication; that follows a known or expected

response pattern to the study medication; and that is confirmed by improvement on stopping or reducing the dosage of the study medication, and reappearance of the reaction on repeated exposure.

If discernible at the time of completing an AE eCRF, a specific disease or syndrome rather than individual associated signs and symptoms should be identified by the Investigator and recorded on the appropriate AE eCRF. However, if an observed or reported sign, symptom, or clinically significant laboratory anomaly is not considered by the Investigator to be a component of a specific disease or syndrome, then it should be recorded as a separate AE on the appropriate AE eCRF.

#### **8.1.3. Reporting of Serious Adverse Events**

When an SAE occurs, the Investigator or designee must log into the electronic data capture (EDC) system and complete the SAE Report form within 24 hours of first becoming aware of the SAE. The SAE will automatically be reported to the Medical Monitor or designee electronically.

Follow-up information relating to a SAE must be reported to the Medical Monitor within 24 hours of receipt by the Investigator by entering new information into the electronic SAE form. The updated SAE will automatically be reported to the Medical Monitor or designee electronically.

If one is unable to log into the EDC system, the SAE hotline may be contacted (information located in the Investigator Site File in the Study Contact list).

All SAEs that occur at a given site should, in addition, be reported by the Investigators to the responsible IRB/EC without undue delay, if applicable according to IRB/EC requirements.

During the conduct of the study, the Sponsor will provide expedited safety reports (AEs classified as serious, unexpected and at least possibly related to investigational product) to the investigative sites as notification of new safety findings. If this occurs, the investigative site must report the information to their IRB/EC per local guidelines (may be submitted by the Sponsor or designee for sites that use a central IRB).

#### **8.1.4. Safety Monitoring Roles**

The site personnel will carefully monitor each patient throughout the study for possible AEs. All AEs will be documented on the eCRF designed specifically for this purpose, and will be followed until either completely resolved or until a stable chronic outcome is determined by the Principal Investigator. SAEs will be reported in accordance with Section 8.1.3.

The Medical Monitor must promptly review all information relevant to the safety of an investigational new product received from any source. The Medical Monitor will also review alert laboratory results in real time and will contact Investigators as needed to ensure that issues are managed in an appropriate manner.

The medical monitor and the Sponsor will review safety data approximately on a quarterly basis, accessed through the EDC system and associated reporting tools, in order to identify potential safety issues/trends that may not be apparent through individual AE reporting. If systematic review identifies a pattern of concern, Sponsor will take steps to address the issues including, but

not limited to, modifying the protocol and/or notifying investigator, authorities and IRB/ECs. Each review will be documented and filed in the Trial Master File.

#### **8.1.5. Clinical Management of Index Knee-related Events**

In the event that the patient has an immediate reaction following administration of study medication or returns to the clinic with an acute exacerbation (e.g., tenderness, increased pain, swelling, effusion, decreased mobility of the index knee), the patient should be treated according to local clinical guidelines and physician experience.

If the index knee is aspirated at any time after administration of study medication for any reason, the volume of synovial fluid aspirated must be documented, synovial fluid should be (1) cultured, (2) evaluated for presence of crystals, and (3) assessed for white cell count at a local laboratory, and the results should be documented.

Any event that is a change from the patient's baseline status (new or worsening case) should be reported as an AE and those meeting the definition of serious must be reported in accordance with Section 8.1.3.

#### **8.1.6. Pregnancy**

All pregnancies occurring during the study will be reported in the same timeframe as SAEs. All reports of pregnancy, including male patients who conceive, must be followed for information regarding the course of the pregnancy and delivery, as well as the condition of the newborn. Follow-up information concerning the outcome of the pregnancy should be provided to the Sponsor in a timely manner. Additional follow-up is not needed when a newborn baby is healthy.

## 9. STATISTICAL CONSIDERATIONS

### 9.1. Statistical and Analytical Plans

A comprehensive statistical analysis plan (SAP) will be written and approved prior to database lock for this study that describes the final analyses to be completed for safety and exploratory efficacy endpoints. If, after the study has been completed, changes are made to the statistical analysis plan referenced below, these deviations to the plan will be listed, along with an explanation as to why they occurred, in the Clinical Study Report (CSR). The key aspects of those analyses are summarized below.

#### 9.1.1. Interim Analysis

No formal interim analysis is planned for the primary safety endpoints in this open-label study to assess the safety and tolerability of FX006 after repeat administration. However, interim analysis may be conducted with exploratory endpoints to examine efficacy signals following administration of one or two doses of 32mg FX006. These interim analyses on exploratory endpoints may be completed for data review, regulatory updates, and/or publication (or presentation at congresses) for this open-label study. Any interim analysis completed will have an interim analysis plan written and approved to describe the purpose and analytical objectives of the interim analysis. Final analyses, described in the protocol and statistical analysis plan, will be conducted after completion of the study, when all subjects have either discontinued the study early (prior to Week 52) or completed the study through Week 52.

#### 9.1.2. Final Analyses

All final analyses will be completed following database lock. Final analyses specified in the protocol and SAP will be completed and reported in the CSR. Interim analyses conducted with exploratory endpoints to examine efficacy signals prior to database lock will also be reported in the final CSR. Post-hoc, or additional exploratory analyses, not defined in the SAP may be completed to further understanding and elucidation of the study results. Any post-hoc, exploratory, analyses completed will be clearly identified as such in the final CSR.

## 9.2. General Considerations and Methods

Data collected in this study will be presented using summary tables, figures, and patient data listings. Summary tables will present data by treatment group and, if applicable, by time of collection. Continuous variables will be summarized using descriptive statistics, specifically the number of patients (n), the mean, median, standard deviation, minimum and maximum, and coefficient of variations (%CV). Categorical variables will be summarized by frequencies and percentages. Confidence intervals will be provided where appropriate for derived endpoints. Figures will be used to support the presentation of certain data. Sensitivity analyses may be performed to examine the effect of missing data, as well as the effect of Baseline imbalance for secondary endpoints.

All confidence intervals (CIs), statistical tests, and resulting p values will be reported as 2-sided. Significance will be assessed at  $\alpha = 0.05$  level and the significance level will not be adjusted for multiple comparisons in the exploratory efficacy endpoint analyses.

### **9.2.1. Analysis Populations**

Three main analysis populations are planned for this study as follows:

- Safety Population: All patients who received study medication. The Safety Population will be used to assess safety and tolerability for the primary endpoint.
- FAS Population: All patients who received study drug and provide at least one post-baseline efficacy endpoint assessment. The FAS population will be used to examine exploratory efficacy endpoints.
- Biomarker Population: All patients who received study medication and provide at least one synovial fluid sample for biomarker analysis.

During the course of this study interim analyses may be completed to examine efficacy signals. Populations utilized for those interim analyses will be clearly defined in an interim analysis plan, and in the final CSR.

### **9.2.2. Study Data**

Study data identified in this protocol are to be collected, and source verified, on eCRF at sites completing the study. All study data will be formulated into data sets to provide transparency, traceability, and integrity of trial analysis results from collection source. Observed study data will be mapped to the Clinical Data Interchange Standards Consortium (CDISC) Study Data Tabulation Model (SDTM) and serve as the source data from the trial. All study analyses will be completed using analysis data sets that are derived from the SDTM and follow the CDISC Analysis Data Model (ADaM) architecture.

#### **9.2.2.1. Clinical Data – CDISC Study Data Tabulation Model (SDTM)**

Domains will be mapped to CDISC SDTM version 3.2. No derived data required for analysis are included in the SDTM domains. All SDTM domains will be fully documented with define documents (DEFINE.XML) and a Study Data Reviewer's Guide (SDRG) after database lock and final analyses are completed.

#### **9.2.2.2. Analysis Data – CDISC Analysis Data Model (ADaM)**

All planned and exploratory analyses will be completed using CDISC compliant ADaM data sets derived from the SDTM domains for this study. Analysis data sets will contain all derived study endpoints required for analysis. All ADaM analysis data sets will be fully documented with define documents (DEFINE.XML) and an Analysis Data Reviewer's Guide (ADRG) after database lock and final analyses are completed.

### **9.2.3. Study Variables for Assessment**

Please refer to Section [7.7.1](#) for study variables for the primary safety endpoint.

### **9.2.4. Sub-Groups and Covariates**

No pre-planned sub-groups are identified for this study. Sub-groups may be defined for interim analyses of exploratory efficacy endpoints. In the final analysis, Sub-groups may also be defined

and explored after all pre-planned analyses have been completed to further elucidate study results.

Covariates for exploratory efficacy analyses will be fully defined in the SAP and interim analysis plans.

### **9.3. Determination of Sample Size**

A sample size of approximately 100 patients who receive two doses of FX006 is considered a reasonable sample size in order to assess the safety profile of repeat administration of FX006. No formal power and sample size calculations have been made as the analysis of the efficacy data collected from this study will be considered exploratory and hypothesis-generating for future multiple dose studies of FX006. In order to ensure at least 100 patients who receive two doses of FX006 are enrolled and followed for 52 weeks, approximately 200 patients will be enrolled based on an estimate that approximately 66% of patients enrolled will be eligible to receive a second dose of FX006 and approximately 75% of subjects who receive a second dose will complete the study through Week 52.

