Study Design and Methodology: This study is an open-label, repeat administration design of 32 mg FX006. The study will be conducted in male and female patients $\geq$ 40 years of age with symptomatic OA of the knee. Eligible patients will be offered participation to receive an initial IA injection of FX006 administered to the index knee at Day 1. Patients who receive an initial injection of FX006 will return at Weeks 4 and 8 before being evaluated at 12, 16, 20, and 24 weeks following the initial administration of FX006 for repeat administration. At the first visit where the patient has been determined to meet repeat administration eligibility criteria described in Section 7.4.3, the patient will be eligible to receive a second IA injection of FX006 administered to the index knee. Patients who are eligible to receive a second injection will be evaluated for a total of 52 weeks post initial injection at: Weeks 4, 8, 12, 16, 20, 24, 28, 32, 36, 40, 44, 48, and 52, regardless of the visit at which they receive their second injection. Patients that do not benefit from the initial treatment as determined by evaluation at Week 12 will complete the study at the Week 12 follow-up visit. These patients will be evaluated for a total of 12 weeks post initial injection at: Weeks 4, 8, 12. Patients who are not eligible for a second injection of FX006 after evaluation at Weeks 12, 16, 20, and 24 will complete the study at the Week 24 follow-up visit. These patients will be evaluated for a total of 24 weeks post initial injection at: Weeks 4, 8, 12, 16, 20, and 24. Refer to Appendix 2 Study Visit Flow Chart . The study is expected to enroll over approximately 6 months.
Number of Patients: Approximately 200 patients will be enrolled to ensure that at least 100 patients receive two doses of 32 mg FX006 and complete the study through Week 52.
Test Product, Dose and Mode of Administration: FX006 – extended release formulation of TA in 75:25 poly(lactic-co-glycolic) acid (PLGA) microspheres. Nominal 32 mg TA, IA, administered as a single 5 mL injection
Reference Compound(s), Dose and Mode of Administration: Not applicable

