**Sample Size Considerations:**

A sample size of approximately 100 patients who receive two doses of 32 mg FX006 is considered a reasonable sample size in order to assess the safety profile of repeat administration of FX006. No formal power and sample size calculations have been made as the analysis of the efficacy data collected from this study will be considered exploratory and hypothesis-generating for future multiple dose studies of FX006. In order to ensure at least 100 patients who receive two doses of 32 mg FX006 are enrolled and followed for 52 weeks, approximately 200 patients will be enrolled based on an estimate that approximately 66% of patients enrolled will be eligible to receive a second dose of 32 mg FX006 and approximately 75% of subjects who receive a second dose will complete the study through Week 52.

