## 7.4. Selection of Study Population

### 7.4.1. Number of Patients

Approximately 200 patients will be enrolled to ensure that at least 100 patients receive two doses of FX006 and complete the study through Week 52.

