#### **7.4.4. Removal of Patients from Therapy or Assessments**

Each patient will be informed of his/her right to discontinue from the study at any time for any reason and without prejudice to alternative treatment. The Principal Investigator may also discontinue a patient from the study at any time if, for example, he/she considers the patient's health to be compromised by remaining in the study, or the study is prematurely terminated. In these cases the Principal Investigator will:

1. attempt to complete the study assessments defined for the Early Termination Visit\*
2. determine whether the patient is willing to be contacted to follow ongoing or new AEs through Week 12 for patients who only receive a single injection, or through Week 52 for patients who receive a second injection (if reason for discontinuation is not "withdrew consent") and contact patient as necessary (via phone or in-person). Concomitant medications associated with any AE will also be captured.
3. document patient consent in the source document for continued follow-up

*\*Note: Early Termination visits should follow the Week 52 visit schedule*

Data collected from discontinued patients will be included in the clinical study report. Patients who discontinue from the study may be replaced at the discretion of the Sponsor.

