#### **4.8. Study Drug Exposure**

Details of study drug administration will be tabulated and presented for the SP by the following groups:

- First (and only) dose for patients receiving one dose
- First dose for patients receiving two doses
- Second dose for patients receiving two doses

The position of knee during injection, approach during injection, whether or not the entire contents of the syringe was injected, reason (if entire contents not injected), the numbing agent used, whether or not ultrasound guidance was used, volume of synovial fluid aspirated, and whether a 20 or 21-gauge needle was used will be presented.

Benefit from the initial dose of FX006 and patients with no major safety concerns during the initial dose period will be summarized for the Week 12 visit. In addition, patients clinically indicated to receive a second dose of FX006 and patients eligible for the second dose at Weeks 12, 16, 20 and 24 will be summarized, as well as the number of patients receiving the second dose at each of these visits. These data come from the “Repeat Dose Eligibility” CRF.

Patients receiving one dose and two doses and the visit at which the second dose was received will be summarized.

A summary of time to second dose will be displayed for patients receiving two doses. The median time to second dose will be estimated based on the 50th percentile of the Kaplan-Meier distribution. Additional summary statistics will be presented, including the 25th and 75th percentiles, and the corresponding 95% confidence intervals.

Additionally, repeat dose data will be presented separately by the following subgroups:

- K-L Grade 2, 3 and 4

- Prior IA steroid injection
- Unilateral/bilateral knee OA
- Prior index knee OA surgery or procedure

All study drug exposure data will be presented in a data listing.

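### Does enrolling about 200 patients really secure at least 100 two-dose patients followed to Week 52?

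*Protocol*

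**What the plan says.** Five places make the statement. The full version is in Protocol 9.3: "In order to ensure at least 100 patients who receive two doses of FX006 are enrolled and followed for 52 weeks", about 200 patients will be enrolled. The estimate given is "approximately 66% of patients enrolled will be eligible to receive a second dose of FX006 and approximately 75% of subjects", the latter being the share of re-dosed patients completing Week 52. The synopsis paragraph on sample size considerations ("In order to ensure at least 100 patients who receive two doses of 32 mg FX006 are enrolled and followed for 52 weeks") and SAP 4.1 repeat it with the same two rates.

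Two shorter versions give no rates. The synopsis entry on number of patients says about 200 will be enrolled "to ensure that at least 100 patients receive two doses of 32 mg FX006 and complete the study through Week 52". Protocol 7.4.1 says "Approximately 200 patients will be enrolled to ensure that at least 100 patients receive two doses of FX006" and complete through Week 52.

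Protocol 9.3 and SAP 4.1 also state that no formal power or sample size calculation was made. They call about 100 patients with two doses a reasonable number for assessing the safety of repeat administration; that adequacy sentence has no Week 52 condition.

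Three further provisions bear on the point:
- Protocol 7.4.4 allows replacement: "Patients who discontinue from the study may be replaced at the discretion of the Sponsor".
- The same section says "Early Termination visits should follow the Week 52 visit schedule" and provides for adverse event contact through Week 52 for two-dose patients who stop early and agree to it.
- SAP Section 5 reports that more than 90% of enrolled patients received a second dose, with about 10 receiving only one.

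**The concern.** Ensuring a minimum implies a high probability of reaching it. A sample size obtained by dividing the target by the expected yield gives only about an even chance, because the target then sits at the centre of the distribution. Here the stated rates put the expected count one below the target.

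The target also looks as if it should matter. The primary objective is the safety of two doses. The end-of-study X-ray is taken only in two-dose patients, and the Per Protocol Imaging Population (SAP 3.1) leaves out early terminations. The number of Week 52 completers therefore caps the denominator of the per-protocol chondrolysis and shift tables. If the plan had promised that number and had an even chance of missing it, a reader might ask for more enrolment or for a corrected statement.

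**Working it through.** **Inputs.** Enrolment about 200; 66% eligible for a second dose; 75% of recipients completing Week 52; target 100 (Protocol 9.3, SAP 4.1). The probabilities below also assume independent patients, enrolment fixed at the stated number, every eligible patient re-dosed, and no replacement.

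**The plan's own figure.** Yield per enrolled patient = 0.66 × 0.75 = 0.495. Required enrolment = 100 / 0.495 = 202. If 66% stands for two-thirds, the yield is 0.50 and the requirement is exactly 200. About 200 is reproduced.

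**Expected counts at 200.**
- Second-dose recipients: 200 × 0.66 = 132. The chance of at least 100 recipients is above 99.99%.
- Week 52 completers: 200 × 0.495 = 99, with SD = √(200 × 0.495 × 0.505) = 7.1.

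**Chance of at least 100 completers (exact binomial).**

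| Case | Yield | Enrolled | Expected | P(≥ 100) |
|---|---|---|---|---|
| Stated rates, 66% and 75% | 0.495 | 200 | 99.0 | 0.47 |
| 66% read as two-thirds | 0.500 | 200 | 100.0 | 0.53 |
| Low rounding limits, 65.5% and 74.5% | 0.488 | 200 | 97.6 | 0.39 |
| High rounding limits, 66.5% and 75.5% | 0.502 | 200 | 100.4 | 0.55 |
| Both rates 2 points lower (assumed) | 0.64 × 0.73 = 0.467 | 200 | 93.4 | 0.20 |
| Both rates 2 points higher (assumed) | 0.68 × 0.77 = 0.524 | 200 | 104.7 | 0.77 |
| 5% of eligible patients not re-dosed (assumed) | 0.66 × 0.95 × 0.75 = 0.470 | 200 | 94.1 | 0.22 |
| Enrolment 195 | 0.495 | 195 | 96.5 | 0.33 |
| Enrolment 205 | 0.495 | 205 | 101.5 | 0.61 |

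The lack of margin is real. The size of the probability is not robust: it moves from about 0.2 to 0.8 on changes that the word approximately easily covers.

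**Effect of replacement.** On the stated rates, 132 × 0.25 = 33 two-dose patients would stop early. Treating replacements as extra enrolment at the same yield, 14 more patients (214) give P = 0.81 and 26 more (226) give P = 0.95.

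**Effect of a shortfall on precision.** One SD below expectation is 99 − 7 = 92 completers. For an event seen in no patient, the approximate upper 95% limit (3/n) is 3/100 = 3.0% with 100 completers and 3/92 = 3.3% with 92.

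**What SAP Section 5 implies.** Total enrolment is not given there, so take 200.
- 90% re-dosed, 75% completing: 200 × 0.90 × 0.75 = 135 expected.
- Only 10 patients with one dose: 190 × 0.75 = 142.5 expected.
- 90% re-dosed, 65% completing (assumed): 200 × 0.90 × 0.65 = 117 expected; P(≥ 100) = 0.99.

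**The case for a change.** The strongest case for a change is that a design statement should be true on its own inputs, and this one is not: 99 is below 100, and neither reading 66% as two-thirds nor allowing for rounding of the rates lifts the chance much above one half. Two of the five places give no rates, so their reader cannot see that the number rests on estimates. Replacement is discretionary and is not in the calculation, so it guarantees nothing. The calculation also favours the plan, because 66% is an eligibility rate and the SAP counts eligible and dosed patients separately (SAP 4.8: "patients eligible for the second dose at Weeks 12, 16, 20 and 24 will be summarized, as well as the number of patients receiving" it). Re-dosing later observed at more than 90% does not make the planning statement correct in retrospect, and SAP 4.1 still carries 66% alongside Section 5. The edit would cost one sentence in each place.

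Much of this stands. The verb is too strong, and a sponsor amending the protocol for other reasons could soften it to an aim and label the two rates in SAP 4.1 as planning assumptions. What does not stand is that anything depends on it. The two short entries summarise fuller statements that disclose the estimates. No analysis, population or decision rule uses the figure of 100 completers. Early terminations follow the Week 52 schedule, and the X-ray tables are also produced for the Safety Population, so a two-dose patient who stops early need not be lost from the safety evidence.

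A heavier rewording could also do harm. Replacing at least 100 with approximately 100 would remove a stated target. Changing followed to complete would narrow it, since Protocol 7.4.4 follows some patients who do not complete. Writing in an even chance would fix a model-dependent probability in the documents, in the same SAP that reports re-dosing far above plan.

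**Conclusion.** The observation is correct but needs no change to the plan. On the stated rates about 200 is an expected-value figure: 99 completers expected, with a chance of 0.47 of reaching 100 (0.53 if 66% means two-thirds). This assumes independent patients, a fixed 200, full re-dosing of eligible patients and no replacement. The enrolment figure itself is sound, the rates behind it are disclosed as estimates, and the adequacy claim concerns about 100 two-dose recipients, for which 132 are expected.

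The cost of falling short would be small: at 92 completers instead of 100, the upper limit for an unseen event moves from 3.0% to 3.3%. On the re-dosing in SAP Section 5, with 200 enrolled assumed and completion between 65% and 75%, the target is reached with more than 99% probability. What remains is a loose verb. Correcting it would change no enrolment, analysis, result or conclusion.
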